Wave 3 of data collection, which includes the local evaluation 6-month post-enrollment follow-up survey, is intended to be collected six months after program enrollment, with data collection efforts focused on five to seven months after program enrollment. However, the timing of the follow-up survey data collection can vary, with some participants taking the survey later than expected (e.g., an email with a survey link is opened and completed months after it was delivered) or earlier than expected (in the case of Franklin CBCF participants who complete their follow-up survey immediately upon release; see below). The tracking process typically begins at least 60 days prior to when a participant is due for a follow-up survey. This allows time for new contact attempts when email addresses are undeliverable and mailings are returned to the sender. The incarcerated population also tends to be a difficult population to get in touch with for various reasons. Someone just released from prison may be focusing on housing and employment needs or their contact information is outdated since they were enrolled into the program.

Waves 1 and 2 of all surveys are administered on paper with participants in person, due to technology restrictions in the prison facilities. Paper surveys are entered onto nFORM and Qualtrics (for the local evaluation surveys) within 72 hours of completion by RIDGE staff who have been certified in protecting human research participants. Paper surveys are securely transported by program staff to the RIDGE offices where they are entered and kept in locked storage.

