The process for follow-up data collection (Wave 3) differs from the other two waves. The MER survey tracking team begins attempts to contact study participants approximately five months after program enrollment using email and text messages as the primary contact methods. Participants are sent a QR code and hyperlink that directs them to the self-administered formatted follow-up survey accessed through Qualtrics. Participants can also complete the follow-up survey over the phone with a member of the MER survey tracking team if they prefer. If initial contact attempts are not successful, the survey tracking team will reach out to secondary contacts that participants have identified and provided contact information for during the study enrollment process. Contact attempts continue for 60 days (until 7 months after program enrollment), after which point the survey tracking team stops efforts to collect follow-up surveys. At this point, program staff are provided a list of participants that the tracking team is

unable to get in contact with. If program staff come in contact with any of the participants on the archived list, they will direct the participants to the follow-up survey. Otherwise, all tracking efforts are complete at that point. All participants who complete a follow-up survey receive a \$50 incentive.

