	Survey Wave 3 (Local evaluation follow-up survey)	Six months after program enrollment; Between three to six months after program enrollment at Franklin CBCF	Online via a QR code or email link; over the phone; in person paper survey if in the eligible Franklin CBCF group	MER Staff or RIDGE facilitator if in the eligible Franklin CBCF group	October 2023 – May 31, 2025 for all locations aside from Franklin CBCF; For Franklin CBCF- May 2024- May 31, 2025

Study group	Data source	Timing of data collection	Mode of data collection	Party responsible for data collection	Start and end date of data collection
Counterfactual (in-person)	Survey Wave 1 (nFORM baseline and local evaluation baseline surveys)	Immediately following informed consent and randomization during orientation	In-person paper survey	RIDGE Staff	April 11, 2023 (or January 2023 for pilot cohort) - November 30, 2024
	Survey Wave 2 (nFORM exit and local evaluation post-surveys)	Six weeks after program enrollment, immediately following the last primary workshop session	In-person paper survey	RIDGE Staff	May 23, 2023 (or February 2023 for pilot cohort) – January 11, 2025
	Survey Wave 3 (Local evaluation follow-up survey)	Six months after program enrollment; Between three to six months after program enrollment at Franklin CBCF	Online via a QR code or email link; over the phone; in person paper survey if in the eligible Franklin CBCF group	MER Staff or RIDGE facilitator if in the eligible Franklin CBCF group	October 2023 – May 31, 2025; For Franklin CBCF- May 2024- May 31, 2025

3. CONSORT diagram

The CONSORT diagram for this impact study (where random assignment occurs after consent) can be found in the appendix to this plan. The data used to complete the CONSORT diagram were pulled on July 22, 2024.

D. Analysis

This section describes the plans for defining the analytic sample, assessing baseline equivalence, cleaning data, handling missing data, and addressing potential crossover and contamination. It also describes the analytic models for estimating program impacts and planned sensitivity analyses.

1. Data preparation

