Because technology restrictions in prison facilities require the administration of paper surveys, it is possible for respondents to answer questions in violation of skip/display logic if they misunderstand the instructions on the paper survey. To err on the side of retaining as much of the sample as possible, we will not deem a response invalid if the participant response to a skip logic question incorrectly (answering "no" instead of "yes") but then proceeds to answer the follow-up question accurately.

Participants who report inconsistencies in the number or age of their child(ren) between nFORM and local evaluation surveys at the same time point will have their answers be assigned as the response they gave on the nFORM ACS or entrance survey.

Outlier values, defined as extremely low or extremely high values that are likely introduced to the dataset due to an input error, for variables such as participant's age, children's age, and income, which participants manually input, will be recoded to the 99th percentile for the sample if necessary. We will top-code any values above the 99th percentile with the average of all values below this threshold.

Duplicate data

In the case of duplicate data, where one participant has taken the same local evaluation survey more than one time, we plan to take the following approach:

- Check for incorrectly entered Client IDs that inaccurately flag surveys as duplicates. Using the name and/or DOB fields on the local evaluation survey, we will check that responses that appear to be duplicates were in fact collected from the same participant multiple times (i.e., are true duplicates). Common instances of this occurring could be if a participant did not finish a survey and re-took it later on, or if they took the follow-up survey twice for the incentive. If the survey is not a true duplicate, we will correct Client IDs as necessary.
- For surveys identified as true duplicates, we will check for completeness. If one duplicate survey is complete while the other is not, we will use the most complete survey to minimize item non-response.
- If both duplicate surveys are equally complete, we will use the first response that a participant submitted, as indicated by the Recorded Date field on the Qualtrics data export. This approach is

only applicable to the follow-up survey. Because program staff enter paper survey data into Qualtrics, there should not be duplicate baseline and post-surveys.

Missing data

Survey nonresponse

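### The rule for duplicate follow-up surveys has no timing criterion, so an early Franklin CBCF form can be analysed in place of the same person's in-window response

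*Combined protocol and SAP*

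**What the plan says.** Section D.1 (Duplicate data) first checks that two surveys really come from the same participant. It then selects in two steps. Completeness comes first: "If one duplicate survey is complete while the other is not, we will use the most complete survey to minimize item non-response". The tie-break follows: "If both duplicate surveys are equally complete, we will use the first response that a participant submitted", with the order taken from Qualtrics' Recorded Date. The section limits this approach to the follow-up survey. Among the ways a duplicate could arise it lists an unfinished survey retaken later, "or if they took the follow-up survey twice for the incentive".

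On timing, both primary research questions (section A.1) and Table 1 place the outcome six months after enrollment. Section C.2 aims Wave 3 at that point, "with data collection efforts focused on five to seven months after program enrollment". For one site, Table 5 gives a different range: "Between three to six months after program enrollment at Franklin CBCF". Section C.2 explains that Franklin participants who join a jobs initiative at release may complete a paper follow-up form shortly before they leave, starting in May 2024. For follow-up in general, the tracking team "begins attempts to contact study participants approximately five months after program enrollment using email and text messages".

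Two other provisions bear on timing. Section D.3 and Table 6 put the number of days from enrollment to follow-up in every outcome model. Section D.4 repeats the analyses on people who completed the follow-up at 5-7 months.

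**The concern.** A rule that chooses between two measurements of the same outcome should favour the one nearer the time the research question names. This rule ranks on completeness and then on order of submission. Once Franklin can collect Wave 3 from month three, the first form submitted may also be the one further from target.

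The route to two forms is not closed in the text. The follow-up eligibility conditions (section C.2 and Figure A.3) are consent plus a baseline survey, and neither place adds that no follow-up has yet been given. The description of tracking does not exclude people who have already handed in a paper form.

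The primary outcomes are employment and financial attitudes. The early form is filled in inside the facility, whereas the later one may be filled in after release, so the two can differ in setting as well as in time. Where both exist, the trial could hold the answer it set out to measure and analyse the other one.

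**Working it through.** The documents give no duplicate rate and no count of early forms, so there is no planned figure to reproduce. The check has three parts.

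**1. The rule applied to pairs of surveys.** Take the highest completeness, and on a tie take the earlier record. The pairs are illustrative.

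| Early form (month, complete) | Later form (month, complete) | Kept | In 5-7 month window? |
|---|---|---|---|
| 3.5, 100% | 6, 100% | 3.5 | No |
| 3.5, 100% | 6, 90% | 3.5 | No |
| 3.5, 90% | 6, 100% | 6 | Yes |
| 5.5, 100% | 6, 100% | 5.5 | Yes |

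The off-target form is kept only when it predates month five and is at least as complete as the later one.

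**2. Whether completeness is needed as the first criterion.** Section D.1 already scores a construct when at least 80% of its items are answered. With one item missing, employment attitudes has 7/8 = 87.5% and financial attitudes 6/7 = 85.7%, so both remain scorable. The duplicate rule speaks of the survey rather than the construct. Read literally, a blank in an unrelated section could decide which employment score is used.

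**3. How many people could be affected.** Inputs from the documents: target analytic sample 768 (section C.1) and Franklin share about 78% (section C.2). This gives 0.78 × 768 = 599 Franklin participants.

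Assumptions not in the documents:
- a share d of Franklin participants give both forms;
- two thirds of paper forms fall before month five, which is (5 − 3)/(6 − 3) if timing is uniform over months three to six;
- the early form is at least as complete in a share k of pairs, between 50% and 100%.

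Displaced responses = 599 × d × 2/3 × k.

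| d | k = 50% | k = 100% | Share of 768 |
|---|---|---|---|
| 0% | 0 | 0 | 0% |
| 1% | 2 | 4 | 0.3-0.5% |
| 5% | 10 | 20 | 1.3-2.6% |
| 10% | 20 | 40 | 2.6-5.2% |

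For a given d these lean high, because the calculation treats all Franklin participants as able to give the paper form. It is offered only to those in the jobs initiative, and only from May 2024.

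**Position of the existing safeguards.** As written, the days-to-follow-up covariate adjusts for the timing of whichever record was kept and cannot bring back a discarded on-time answer. Section D.4 does not say whether duplicates are re-selected for the 5-7 month analysis. If they are not, a person whose early form was kept drops out of it despite having an in-window form.

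**The case against.** The strongest reply is that nobody may ever hold both forms. Section C.2 presents the Franklin form as an alternative procedure to raise response, not an extra wave. Section C.1 ends active participation when the follow-up survey is completed, and response is monitored every two weeks, so completers are known. The remark about repeat surveys is hedged and does not describe a paper form followed by an online one. This stands: the documents do not show that displacement has happened, and the absence of an exclusion from tracking is silence, not evidence.

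It is also fair that a more complete on-time form wins under the present rule, that Franklin forms from months five to six are already in window, and that the plan openly acknowledges early Franklin surveys, adjusts for timing and runs a window-restricted analysis. Someone with an in-window form could even be said to meet the literal wording of section D.4, so the loss from that analysis is an ambiguity rather than a certainty.

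A reader might infer that early Franklin forms routinely replace on-time answers, that two thirds of duplicates are affected, or that the treatment comparison is biased. None of this is supported. The two-thirds figure is an assumed share of paper forms, not of duplicates or of the sample. Section C.2 states that process and timing are the same in both arms, and nothing in the documents points to a difference between arms in duplicates.

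Finally, keeping the first response is pre-specified, ignores study arm, and protects against repeats made for the incentive. That is a real merit, and any replacement rule gives up some of it.

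**Conclusion.** The gap in the rule is clear from the text: neither step refers to six months or to the 5-7 month window. Given a Franklin form from before month five, an in-window form from the same person, and an early form at least as complete, the primary analysis uses the off-target answer. The covariate mitigates this only in part, and the sensitivity analysis may lose the same person.

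The size is unknown and may be zero. The range of 0 to about 40 people (0 to 5.2% of 768) rests entirely on the assumed duplicate rates, uniform paper-form timing and the assumed completeness shares. Confidence is high that the timing criterion is missing and low on how often it matters.

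A secondary point is an inference. Recorded Date for a paper form entered by staff may reflect data entry rather than completion. The 72-hour entry rule in section C.2 is stated for Waves 1 and 2, and no entry deadline is given for Wave 3 paper forms, so even the order of two forms could be wrong.

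This is a modest correction to a stated rule, worth making before analysis.

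**What to change.** Replace the last two selection steps in section D.1 as follows. Among true duplicate follow-up surveys that meet the 80% item threshold for both primary constructs, use one survey per person for both outcomes: the one completed closest to six months after enrollment. Because 5-7 months is symmetric about six, this always prefers an in-window form to one outside it. Let completeness decide when only one form meets the threshold, and use the earlier form only as a tie-break.

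Three additions go with this:
- Order forms, and compute days to follow-up, by the date the participant completed the form where that is recorded. Use Recorded Date only otherwise.
- State in section D.4 that the 5-7 month analysis uses the same selection, and in section C.2 whether early Franklin completers are still contacted at five to seven months.
- Report the number of duplicates by arm and repeat the primary analysis with the first response, since a later form may be a repeat taken for the incentive.

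The cost is a few sentences and a few lines of R. No new data collection is needed, but the date ordering depends on a completion date being available for paper forms, which the documents do not confirm. Table 5 has Wave 3 running to May 31, 2025, so a plan dated August 22, 2024 leaves time to settle this before analysis.

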Because outcome measures for this impact study are constructed from survey items from both nFORM and the local evaluation surveys, survey nonresponse on either the nFORM baseline survey, local evaluation baseline survey, nFORM exit survey, local evaluation post survey, or local evaluation follow-up survey can lead to sample attrition. Survey response rates are monitored on an ongoing basis through bi-weekly CQI reports produced by the evaluation team using the nFORM Survey Completion Summary operational report and Qualtrics response data export feature. Response rates are calculated by dividing the number of participants who responded to each survey by the number of participants who were eligible to respond to that survey up to that time point. If CQI reports show that survey response rates are below intended targets, the CQI team brainstorms and implements strategies to increase response rates to minimize sample attrition caused by survey nonresponse. Reasons for survey nonresponse, to the degree that they are known, will be reported in the CONSORT diagram. Individuals with survey nonresponse at the follow-up time point will not be included in the analytic sample; the analysis for each outcome will use complete case data.

Item nonresponse

Item nonresponse can also lead to sample attrition for particular outcome measures if participants skip survey items that are aligned with the research questions for this study. Item nonresponse is calculated by dividing the number of participants who respond to a survey item by the number who were eligible and able to answer a question based on skip/display logic. As stated in the data preparation section above, respondents taking paper surveys may violate skip/display logic, and invalid responses will be dropped before item-level response rates are calculated. We will also note what proportion of the sample skipped out of the relationship and employment attitude questions to give context to the item nonresponse.

Constructed outcome measures

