Analyses will be conducted using the R Studio statistical software package. The basic model for this impact evaluation will include a dummy variable for intervention group assignment, equal to 1 if a participant was randomly assigned to receive the curriculum on-demand via tablet, and a participant's score at baseline as the main predictors of each outcome measure at follow-up. To enhance the precision of the impact estimates, we plan to include several other covariates in our models. For all outcome analyses, we will control for participant age, gender, and race, as well as the timing of a participant's follow-up survey (number of days between program enrollment and follow-up survey completion). We will also consider including a facility indicator to denote which site the participant received services at. Additionally, we will include any demographic variables that were shown to be significantly different between study groups during baseline equivalency analysis. For the healthy relationship attitudes outcome, we also plan to include relationship status at baseline as a covariate. This will only be available if a participant reports being in a relationship at baseline and at follow-up.

Table 6. Covariates included in impact analyses

Covariate	Description of the covariate
Age	Age (in years) as of the baseline data collection, as reported on the ACS
Gender	Self-reported gender identification as of the baseline data collection, as reported on the ACS
Race	Self-reported racial identification as of the baseline data collection, as reported on the ACS

Covariate	Description of the covariate
Timing of follow-up survey	Number of days between program enrollment date and date of follow-up survey completion to control for variation in survey timing
Relationship status (relationship attitude and behavior outcomes only)	Relationship status (1 = in a committed relationship, 0 = not in a committed relationship) as of the baseline data collection, as reported on the ACS

4. Sensitivity analyses for primary research questions

We plan to conduct several sensitivity analyses to test the robustness of our results. First, and as mentioned earlier in the plan, we will conduct a sensitivity analysis to see if and how our outcome construct measures change if we use 70% as a threshold for non-missing items instead of 80% as a threshold.

[figure not shown]

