Next, we will conduct an analysis to see how outcome construct measures change if we use mean imputation to replace missing items in the multi-item scales used to create our outcome variables. This is the mean based on observed values from the rest of the sample for that item. The current plan is not to use any imputation for outcome measures, including constructed outcomes from multiple survey items, and instead to make the denominator for the calculation of the average score be equal to the number of non-missing items in that construct.

Finally, we plan to conduct a sensitivity analysis regarding the timing of the follow-up survey. Given changes in follow-up data collection protocol at Franklin CBCF, we anticipate that some respondents will have taken their paper follow-up survey earlier than intended. The sensitivity analysis will repeat our analyses using only people who completed their follow-up survey within the intended data collection window (5-7 months post-enrollment).

5. Analyses addressing secondary research questions

The analytic approach for answering the secondary research question about partner relationship behaviors will be the same as the approach taken for the primary research questions.

Figure A.3. CONSORT diagram for individual clients, for studies in which consent occurred before assignment

Eligible for 6-month post-enrollment follow-up (n = 206)

To be eligible, a participant must have provided consent and taken either the nFORM baseline or local evaluation baseline survey

Completed follow-up (n = 64)

Data collection: July 1, 2023-July 22, 2024

Reasons for non-completes (n = 1) (that can be accounted for)

Consent revoked (n = ___), declined survey (n = ___), deceased (n = ___), dropped out (n = 7), moved (n = ___), incarcerated (n = 1)

Eligible for 6-month post-enrollment follow-up (n = 190)

To be eligible, a participant must have provided consent and taken either the nFORM baseline or local evaluation baseline survey

Completed follow-up (n = 52)

Data collection: July 1, 2023-July 22, 2024

Reasons for non-completes (n = 1) (that can be accounted for)

Consent revoked (n = ___), declined survey (n = ___), deceased (n = ___), dropped out (n = 4), moved (n = ___), incarcerated (n = 1)

Figure A.4. Survey items linked to research questions

Measure	Item Response	Are these items linked to a primary research question?	Are these items linked to a secondary research question?
Partner relationship beliefs 8 items			No

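### At the July 2024 data pull about 71% of participants listed as eligible had no six-month survey, and no planned sensitivity analysis addresses survey nonresponse

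*Combined protocol and SAP*

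**What the plan says.** Section D.1 (Survey nonresponse) leaves follow-up nonresponders out of the analytic sample, and "the analysis for each outcome will use complete case data". Section D.2 also requires a non-missing baseline value and rules out imputing baseline or outcome data.

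Figure A.3 gives the follow-up counts for the two groups in turn (the text reviewed does not show which group is which):

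- first group: "Eligible for 6-month post-enrollment follow-up (n = 206"; "Completed follow-up (n = 64"
- second group: "Eligible for 6-month post-enrollment follow-up (n = 190"; "Completed follow-up (n = 52"

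Its definition of eligibility does not mention elapsed time: "To be eligible, a participant must have provided consent and taken either the nFORM baseline or local evaluation baseline survey". Section C.3 dates the counts to July 22, 2024.

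Three provisions bear on attrition. D.2 compares it with the What Works Clearinghouse (WWC) cautious threshold. D.2 also checks baseline equivalence between groups, with adjustment for moderate differences and caveats for large ones. D.3 adjusts every model for baseline score, age, gender, race and survey timing.

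D.4 opens with "We plan to conduct several sensitivity analyses to test the robustness of our results" and lists three analyses: a 70% item threshold, mean imputation of missing items, and restriction to surveys taken at 5-7 months.

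**The concern.** People with no follow-up survey are by far the largest block of missing primary-outcome data, and the sensitivity section says nothing about them.

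Nonresponse related to the outcomes is plausible. Section C.2 says that recently released people may be preoccupied with housing and work or have outdated contact details, and the primary outcomes are employment and financial attitudes. If responders and nonresponders differ in ways the model does not capture, and differ more in one arm than the other, the complete-case contrast is biased. If only the treatment effect differs between them, the estimate describes responders and not everyone randomized. In either case the planned checks could all agree with the main result and still say nothing about this risk.

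**Working it through.** **Inputs.** Figure A.3: 64 of 206 and 52 of 190 completed. The plan states no response rate, so there is no figure of its own to reproduce.

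**Nonresponse = 1 - completed/eligible.**

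| | Completed | No survey |
|---|---|---|
| First group | 64/206 = 31.1% | 142/206 = 68.9% |
| Second group | 52/190 = 27.4% | 138/190 = 72.6% |
| Both | 116/396 = 29.3% | 280/396 = 70.7% |

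The completion rates differ by 31.1 - 27.4 = 3.7 points. The standard error is √(0.311×0.689/206 + 0.274×0.726/190) = 0.0457, so the 95% CI is -5.3 to 12.7 points. The figure's itemized reasons cover at most 7 + 1 + 4 + 1 = 13 of the 280 (4.6%).

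**If not all 396 were due.** The documents do not give the number due, so these denominators are assumptions:

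- 300 due: 1 - 116/300 = 61% nonresponse
- 242 due: 1 - 116/242 = 52% nonresponse

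In the other direction, these rates count missing surveys only. A completer also needs a baseline value and 80% of the items.

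**What each D.4 analysis can reach.**

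- *70% item threshold:* changes which returned surveys are scored. It adds no one without a survey.
- *Item-mean imputation:* fills gaps within scales. The plan says of the fill-in value: "This is the mean based on observed values from the rest of the sample for that item". It is described for items within a scale, not for absent surveys.
- *5-7 month window:* keeps a subset of responders. Table 5 places Franklin CBCF follow-up at three to six months, and C.2 says that site enrolls about 78% of participants, so this step may remove many of them.

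**Size, for illustration only.** The plan states no effect size. I assume 0.20 SD in responders, which is about what 384 per group would detect with 80% power at two-sided 5% (both assumed): 2.80 × √(2/384) = 0.202.

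With response rate r, the overall effect is r × (responder effect) + (1 - r) × (nonresponder effect). It is zero when the nonresponder effect equals -0.20 × r/(1 - r):

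- r = 116/396 (29%): -0.20 × 116/280 = -0.083 SD
- r = 116/300 (39%): -0.20 × 116/184 = -0.126 SD
- r = 116/242 (48%): -0.20 × 116/126 = -0.184 SD

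If nonresponders had no effect at all, the overall effect at 29.3% response would be 0.20 × 0.293 = 0.059 SD.

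A separate case is selection in one arm only. If nonresponders in one arm differ from that arm's responders by an assumed 0.20 SD in mean score, the contrast shifts by 0.20 × 0.689 = 0.138 SD or 0.20 × 0.726 = 0.145 SD, depending on the arm. At 52% nonresponse the shift is 0.20 × 126/242 = 0.104 SD.

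**The case against.** The strongest reply is that the plan does deal with attrition. A reader of D.4 alone might infer that it is never examined. D.2 does not support that: it applies the WWC threshold and compares the arms on demographics and baseline outcomes, which, if run on the analytic sample, would pick up measured traces of arm-differential response. D.3 goes further. If response depends only on arm and the model's covariates, and the model is correct, complete-case regression already estimates the arm effect consistently. This stands, and it limits what weighting or imputation on the same covariates could add. But the threshold only classifies, and the weighting mentioned in D.2 is for imbalance between arms. A facility indicator is only to be considered, Wave 2 completion is not used, and unmeasured causes of nonresponse are left alone.

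The second reply is that the 71% is not final. This is right. Follow-up runs to May 31, 2025, contact attempts continue to seven months after enrollment, and the Franklin paper procedure, meant to raise response, was set to begin only in May 2024. D.1 computes response rates among those eligible up to the time point, which suggests the 396 were due, but Figure A.3 does not say so.

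Third, nothing here demonstrates bias. The 3.7-point difference is compatible with none. A reader might infer that response is known to vary by site or release route, but the documents give no rates by either, and the Franklin procedure applies to both arms.

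**Conclusion.** The point holds as a gap in the sensitivity analyses. At the July 22, 2024 pull, 70.7% of those listed as eligible had no follow-up survey. Under the assumed smaller denominators the figure is 52% to 61%, still very high. The omission does not depend on the exact rate: the plan produces no estimate of either primary effect under any other assumption about nonresponders.

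The documents do not support reading this as proof that the complete-case result is biased, as a final attrition rate, or as a plan with no attrition provision. The cancelling effects of -0.08 to -0.18 SD rest on an assumed 0.20 SD in responders. They show how far a conclusion could depend on people not observed, not what those people's outcomes are.

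**What to change.** Leave the primary analysis and the three existing sensitivity analyses unchanged. Add to D.4, for both primary outcomes:

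1. **Response-weighted regression.** Fit the complete-case model with inverse-probability-of-response weights. Model response on arm, baseline composite, age, gender, race, facility (sparse categories collapsed), baseline relationship status, Wave 2 completion, and whether the participant's follow-up fell due under the Franklin paper procedure. Wave 2 completion is measured after enrollment, so label it an auxiliary variable. Timing relative to the Franklin change should be set by when follow-up fell due and not by enrollment date, because the procedure acts at release. Use robust standard errors and check for extreme weights.
2. **Multiple imputation with a delta shift.** Impute missing follow-up composites by arm, then apply a tipping-point shift that can differ by arm. This is the part that relaxes the assumption that response depends only on measured variables.

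Report both beside the complete-case estimate, with the final response rate by arm.

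The cost is a little more analysis on data the study already collects. Collection was to run to May 31, 2025, so both analyses could be specified before the final data. The downsides are wider intervals, possibly unstable weights with few responders, and heavy model dependence when most outcomes are imputed. The results should therefore be presented as sensitivity analyses, not as replacements for the main estimate.
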